14.1.4. SENSITIVITY ANALYSIS OF PRIMARY EFFICACY VARIABLE(S)

- Sensitivity to missing data assumptions
 - A sensitivity analysis imputing missing placebo subjects as Responders instead of Non-Responders will be performed.
- Sensitivity to adjustment for covariates

Document:	x:\biostatistics\documentation\sap\pya18238_izana_izn-101	_sap_v1_0_2019050.docx	
Author:		Version Number:	1.0
		Version Date:	07May2019
Template No.	CS_TP_BS016 Revision 5	Reference: CS_WI	_BS00

Effective Date: 01Apr2018

- A sensitivity analysis including the stratification as covariate will be performed.
- o Sensitivity to analysis set
 - The primary analysis will be repeated for the COM and PPAS analysis set.

14.2. SECONDARY EFFICACY

The secondary efficacy analyses will be performed for FAS and PPAS.

14.2.1. SECONDARY EFFICACY VARIABLES & DERIVATIONS

14.2.1.1. Proportion of subjects who achieve an ASAS40 clinical response at Week 12

ASAS40 responder is defined as follow:

A subject with an improvement from baseline of at least 40% and an absolute improvement of at least 20 units on a 0-100 VAS scale in at least 3 of the following four domains derived on the eCRF and no worsening at all in the fourth domain:

- o Subject's Global Assessment of Disease Status,
- Subject's Assessment of Spinal Pain,
- Function (overall BASFI score),
- Inflammation, (average of the last 2 questions of BASDAI: intensity of morning stiffness, duration of morning stiffness)

The data used to calculate ASAS40 are collected in the eCRF at Baseline and Visit 6 (week 12).

14.2.1.2. Proportion of subjects who achieve an ASAS20 clinical response at Week 6

ASAS20 responder is defined as described in the primary efficacy endpoint Section 14.1.1

14.2.1.3. Proportion of subjects who achieve ASDAS-CRP response at Weeks 6 and 12

ASDAS-CRP scores is derived in the eCRF (according to the formula defined in Section 8.1 of

Document:	x:\biostatistics\documentation\sap\pya18238_izana_izn-101	_sap_v1_0_2019050.docx	
Author:		Version Number:	1.0
		Version Date:	07May2019
Template No.	CS_TP_BS016 Revision 5	Reference: CS_W	_BS00

Effective Date: 01Apr2018

the protocol).

The disease activity states are defined as follows:

ASDAS-CRP score	Activity states
<1.3	Inactive disease
\geq 1.3 and <2.1	Moderate disease activity
\geq 2.1 and \leq 3.5	High disease activity
>3.5	Very high disease activity

14.2.2. MISSING DATA METHODS FOR SECONDARY EFFICACY VARIABLE(S)

Subjects with missing primary endpoint data (either at Baseline or Week 12) will be treated as non-responders.

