9.4.1.1 Handling of Missing Data

Non-responder imputation will be used for missing data in the FAS. Missing data will be excluded from analysis in the PP Analysis Set.

Missing data will not be imputed in the Safety Analysis Set.

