9.4.4 Missing Data

Data from subjects who withdraw from the study, including AEs and any follow-up, will be included in the analyses of primary and secondary outcomes.

Missing data (including those due to early discontinuations) will be imputed by a non-responder imputation (NRI). The NRI will be the primary imputation method for handling the missing data.

As a sensitivity analysis, the analysis will also be performed on completers only.

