14.1.2. MISSING DATA METHODS FOR PRIMARY EFFICACY ENDPOINT

Subject with missing primary endpoint data (either at Baseline or Week 12) will be treated as non-responders.

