14.3.2. MISSING DATA METHODS FOR EXPLORATORY EFFICACY VARIABLE(S)

No imputation for missing data will be used for the exploratory endpoints with the exception of the endpoints related to ASAS and ASDAS-CRP responder that will follow the same rule used for the primary and secondary analysis (i.e. subject with missing data at the timepoint of interest will be considered as non-responder).

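### SAP 14.2.2 judges missingness for the Week 6 secondary endpoints by the Week 12 primary data, so read literally an observed Week 6 response can be scored as non-response

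*SAP*

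**What the plan says.** The primary rule in SAP 14.1.2 reads: "Subject with missing primary endpoint data (either at Baseline or Week 12) will be treated as non-responders". SAP 14.2.2, headed for the secondary variables, repeats it almost unchanged: "Subjects with missing primary endpoint data (either at Baseline or Week 12) will be treated as non-responders". It makes no exception for any endpoint or visit.

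SAP 14.2.1 lists ASAS40 at Week 12 and two endpoints that involve Week 6: "Proportion of subjects who achieve an ASAS20 clinical response at Week 6" and "Proportion of subjects who achieve ASDAS-CRP response at Weeks 6 and 12". They are compared by Fisher's exact test (SAP 14.2.3.1) on the FAS and the per-protocol set, PPAS (SAP 14.2).

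SAP 14.3.2 says that the exploratory ASAS and ASDAS-CRP responder endpoints follow the rule of the primary and secondary analyses, and explains that rule as: "subject with missing data at the timepoint of interest will be considered as non-responder".

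Protocol 9.4.1.1 says "Non-responder imputation will be used for missing data in the FAS" and "Missing data will be excluded from analysis in the PP Analysis Set". Protocol 9.4.4 adds that data from subjects who withdraw are to be used in the primary and secondary outcomes. SAP 3.3, which lists changes from the protocol, declares none on this point.

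**The concern.** For a Week 12 endpoint the wording works. For a Week 6 endpoint it asks about the wrong visit: an assessment that was made and met the response criterion is overwritten because a later visit is missing. That goes beyond imputing missing data, because it discards observed data.

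The rule also asks about the wrong variables for ASDAS-CRP. Primary endpoint data include BASFI, which the ASDAS-CRP formula in Protocol 8.1 does not use, and exclude CRP, which it does.

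At stake are the FAS Week 6 responder counts. SAP 14.2.2 and 14.3.2 each purport to state the secondary rule, and a programmer could follow either. Under SAP 4.2 an unblinded team runs the secondary endpoints once all subjects have completed Week 12, and choosing between the two rules after that would be a post-hoc choice.

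**Working it through.** **Rules side by side, for a FAS subject and a Week 6 endpoint**

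| Data pattern | SAP 14.2.2, literal | SAP 14.3.2 |
|---|---|---|
| Week 6 response observed, Week 12 primary data missing | non-responder | responder |
| Week 6 missing, Week 12 complete | not addressed | non-responder |
| Both missing | non-responder | non-responder |
| ASDAS-CRP computable, only BASFI missing at Week 12 | ASDAS-CRP non-responder at Weeks 6 and 12 | scored on its own data |
| CRP missing at the visit, ASAS20 data complete | not addressed | non-responder |

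The general non-responder rule in Protocol 9.4.1.1 and 9.4.4 covers the two gaps, but 14.2.2 itself does not.

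**Analysis sets.** FAS membership needs only randomisation and one dose (SAP 5.3), so Week 12 data can be absent. The PPAS lies within the completers set (COM), which requires Week 12 efficacy data (SAP 5.4, 5.5). That removes most of the problem there. It does not require every ASAS20 component at Week 12, or Baseline data, so a PPAS subject with partial Week 12 or missing Baseline components could still trigger 14.2.2.

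**Early leavers.** Protocol 1.3 (footnote 2) sends them to the EoT/ET visit, which the schedule lists as Visit 6, Week 12. SAP 6.3 maps early-termination data to the next visit number, but says so only for by-visit summaries.
- If the data stay at Visit 6, those who skip that visit or are incomplete there are affected.
- If the 6.3 mapping is applied to responder endpoints, leavers between Weeks 2 and 6 map to Week 6 and leavers between Weeks 6 and 10 map to Week 10. Both groups then lack Week 12 data and are affected. Leavers after Week 10 map to Week 12 and are not.

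**Size.** The plan has no figure to reproduce here, so this is an illustration.

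Inputs from the documents: 36 namilumab and 6 placebo subjects (Protocol 9.2); a two-sided 5% level (SAP 6.5); design rates of 0.6 and 0.3, which are Week 12 ASAS20 rates (Protocol 1.1).

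Assumptions: those rates also hold at Week 6; a share m has Week 6 but not Week 12 data; m runs from 2.5% to 15%, is equal in both arms and is unrelated to response.

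Formulas:
- understatement of a rate = m × rate
- difference under 14.2.2 = 0.30 × (1 − m)
- chance that at least one placebo responder is rescored = 1 − (1 − 0.3m)^6

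Worked case, m = 10%: namilumab loses 0.10 × 0.6 = 6.0 points, or 0.06 × 36 = 2.16 subjects. Placebo loses 0.10 × 0.3 = 3.0 points. The difference is 0.54 − 0.27 = 0.27. The placebo chance is 1 − 0.97^6 = 16.7%.

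| m | Namilumab loss, points (subjects) | Placebo loss, points | Difference | Fisher power | Placebo responder rescored | Rules differ at 5% |
|---|---|---|---|---|---|---|
| 0 | 0 | 0 | 0.30 | 0.194 | 0 | 0 |
| 2.5% | 1.5 (0.54) | 0.75 | 0.2925 | 0.179 | 4.4% | 3.1% |
| 5% | 3.0 (1.08) | 1.5 | 0.285 | 0.166 | 8.7% | 5.6% |
| 10% | 6.0 (2.16) | 3.0 | 0.27 | 0.142 | 16.7% | 9.4% |
| 15% | 9.0 (3.24) | 4.5 | 0.255 | 0.120 | 24.1% | 12.1% |

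Power is exact. The last column is from 400,000 simulated trials, and exact enumeration agrees to within 0.1 point. It counts both directions: at m = 15%, 9.7% go from significant to not and 2.4% the other way. One rescored placebo responder moves that arm by 1/6 = 16.7 points.

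If affected subjects respond at half these rates (0.3 and 0.15), with overall rates held at 0.6 and 0.3, the namilumab loss is 0.75 to 4.5 points, power is 0.186 to 0.154, and the rules differ in about 1.6% to 7.7% of trials.

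Single data sets show that the verdict is sensitive only near the threshold. With one of six placebo responders, 24/36 gives p = 0.032 and 23/36 gives p = 0.068. Near the planned rates, 22/36 and 21/36 against 2/6 both give p = 0.38.

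**The case against.** The strongest reply is that the SAP answers the question itself. Section 14.3.2 explains what the primary and secondary rule means, and its explanation is visit-specific; 14.2.2 looks like a sentence copied from 14.1.2. On intent this stands. But 14.3.2 governs exploratory endpoints and does not amend 14.2.2, which is the section headed for the secondary variables and gives a programmer written authority for the literal reading.

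Second, Protocol 9.4.1.1 names no visit, so a reader who infers a direct contradiction of the protocol goes too far. The conflict is by implication: non-responder imputation is for missing data and an observed Week 6 response is not missing. The sentence on withdrawn subjects in 9.4.4 is the better support.

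Third, the size is hypothetical. No dropout rate or Week 6 response rate is given, leavers may well respond less often than stayers, and the affected group shrinks if most leavers attend the EoT/ET visit and its data stay at Week 12. Power is only 0.19 with nothing missing. The ASAS20 rates say nothing about ASDAS-CRP, for which SAP 14.2.1.3 gives activity states but no response cut-off. All of this stands and limits the severity.

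**Conclusion.** The fault is real and minor. As written, 14.2.2 applies a Baseline-or-Week-12 test on primary endpoint data to Week 6 endpoints, and to an ASDAS-CRP score built from partly different variables. It conflicts with SAP 14.3.2 and, by implication, with Protocol 9.4.1.1 and 9.4.4.

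The main effect is on the FAS Week 6 rates. The shift of 1.5 to 9 points in the namilumab rate, and the chance of a changed 5% verdict of about 3% to 12% (about 1.6% to 7.7% at half response), rest on the assumed 2.5% to 15% affected and on the design rates holding at Week 6.

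Three stronger readings are not supported:
- That the primary result is at risk. It is a Week 12 endpoint with its own matching rule in 14.1.2.
- That only FAS subjects with Week 6 but no Week 12 visit are affected. A missing BASFI alone can cost an ASDAS-CRP response, at Week 12 as well as Week 6.
- That the PPAS is wholly immune. It is largely protected, because completer status requires Week 12 efficacy data, but partial Week 12 or missing Baseline components remain possible.

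**What to change.** Replace the sentence in SAP 14.2.2 with:

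*In the FAS, subjects missing the data needed for the endpoint (including CRP for ASDAS-CRP) at Baseline or at the visit analysed (Week 6 or Week 12) are non-responders for that endpoint; in the PPAS, missing data are excluded, as in protocol 9.4.1.1.*

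This should be in place before the unblinded Week 12 analysis. It costs one sentence, needs no new data and places no burden on subjects.

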14.2.3. ANALYSIS OF SECONDARY EFFICACY ENDPOINTS

14.2.3.1. Analysis of Secondary endpoints 1, 2 and 3

The secondary endpoints will be analysed by means of the Fisher exact test (to account for the small size of the placebo sample). The null hypothesis is that there is no difference in the response rate between the two treatments.

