The study will consist of a maximum 4-week Screening Period, followed by a 12-week double-blind treatment evaluation period, followed by a 16-week safety follow-up period, for a maximum study duration of approximately 32 weeks or 224 days per subject. Eligible subjects will be randomised on Day 1 of Week 0 and receive study treatment administered sc on Day 1 of Week 0, Week 2 (loading dose), Week 6 and Week 10. Subjects will return on Week 12 for an End of Treatment (EoT) visit during which efficacy and safety assessments will be performed. Subjects will have a follow-up visit 16 weeks after the EoT visit.

Number of Investigators and Study Centres:

Up to 10 Investigators and 10 study centres are expected to participate in this study.

Number of Subjects:

Approximately 70 subjects will be screened to achieve 42 subjects randomly assigned to study treatment (36 on active treatment and 6 on placebo) and 42 evaluable subjects for an estimated total of 36 evaluable subjects on the active treatment arm and 6 evaluable subjects in the placebo treatment arm.

Treatment Groups and Duration:

Test product, dose and mode of administration:

Namilumab 150 mg sc administered at Weeks 0, 2, 6 and 10.

Reference therapy, dose and mode of administration:

Matching placebo solution sc administered at Weeks 0, 2, 6 and 10.

Statistical Methods:

The primary endpoint will be ASAS20. Based on literature data, the prior for the placebo and namilumab groups will follow a beta distribution with mean of 0.3 and 0.6, respectively. Weighting for the priors will be equivalent to 20 and 5 subjects, respectively. Sample size is the smallest sample size so that P{ θ act > θ pbo| Y(HA)} >0.927 with probability 0.9, assuming true response rates of 0.3 and 0.6 for the control and namilumab arms, respectively. For a 6:1 randomisation, 42 patients need to be randomised.

Efficacy endpoints will be summarised by treatment group and visit. The posterior distribution of the primary endpoint will be computed using the conjugate priors, and the mean, standard deviation, and 5th, 10th, 25th, 50th, 75th, 90th, and 95th percentiles of the posterior distribution will be presented.

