9.2 Sample Size Determination

The placebo prior = beta(p=0.3, n=20), and the prior for active is beta(p=0.6, n=5). The sample sizes are the smallest n such that the median Q(P{ $\theta_{act} > \theta_{pbo}$ | Y(H_A)}, 1 - γ) > Q(P{ $\theta_{act} > \theta_{pbo}$ | Y(H₀)}, γ), where Q(f, γ) represents the γ quantile from the distribution f, and Y(H_A) represents data generated under the alternative hypothesis, and Y(H₀) represents data generated under the null hypothesis. Sample sizes are shown in Table 9. The recommended sample size is 42 (6 on placebo, 36 on active). A plot of the distribution of P{ $\theta_{act} > \theta_{pbo}$ | Y} with both hypotheses overlapping as a function of the total sample size is shown in Figure 4.

Table 9 Sample Sizes for 6:1 Randomisation, Based on the Parameter y

γ	N Placebo	N Active	N Total
0.80	2	12	14
0.85	4	24	28
0.90	6	36	42

Figure 4Distribution of Posterior Probability $P(\theta_{act} > \theta_{pbo})$ as a Function of Total
Sample Size, Under Both Hypotheses

Shaded areas represent the middle 80% of the distribution (between the 10th and 90th percentiles).

9.3 **Populations for Analyses**

For purposes of analysis, the analysis sets in Table 10 are defined. For efficacy analyses, the Full Analysis Set (FAS) will be the primary analysis set, and the Per Protocol (PP) Analysis Set will be secondary. For safety analyses, the Safety Analysis Set will be the primary analysis set.

Analysis Set	Description		
Entered Analysis Set	All subjects who sign the ICF.		
Randomly Assigned to Study Treatment Analysis Set	All subjects in the Entered Analysis Set who are assigned to study treatment.		
Full Analysis Set	All subjects randomly assigned to study treatment and who take at least 1 dose of study treatment and have specific post-baseline assessments available.		
Per Protocol	All subjects in the Full Analysis Set that have week 10 efficacy data.		
Completer Analysis Set	All subjects in the Full Analysis Set who complete the study.		
Safety Analysis Set	All subjects randomly assigned to study treatment and who take at least 1 dose of study treatment. Subjects will be analysed according to the treatment they actually received.		

Table 10Analysis Sets

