9.4.1 Efficacy Analyses

Endpoint	Statistical Analysis Methods
Primary	The primary endpoint ASAS20 will be assessed using a Bayesian analysis. The control arm will have a beta prior with parameters rate = 0.3 and v = 20, and the namilumab arm will have a beta prior with rate 0.6 and v = 5. Posterior distributions will be calculated, and parameter distributions shown. The mean, standard deviation, and 5 th , 10 th , 25 th , 50 th , 75 th , 90 th , and 95 th percentiles of the posterior distribution will be presented. The posterior distribution will also be presented graphically. Given the observed data, the posterior probability $\eta \equiv P(\pi_{nam} > \pi_{pbo})$ will be calculated (Raineri 2014) and presented. Values of $\eta > 0.927$ will provide strong evidence that namilumab exhibits therapeutic benefit relative to placebo control. Missing data will be treated as non-responders for this analysis. For assessment of robustness of the analysis, the analysis will be performed on Completer Analysis Set.
Secondary	Summary statistics of ASAS20, ASAS40 and other efficacy endpoints will be summarised by visit
~ contain y	and treatment group. Summary statistics will be provided on both the Full and PP Analysis Sets.
Exploratory	Statistics used to summarise these endpoints will be described in the SAP.

Table 11Efficacy Analyses

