3. STUDY DESIGN

3.1. GENERAL DESCRIPTION

Overall Design:

This is a proof-of-concept, randomised, double-blind, placebo-controlled, multi-centre study designed to evaluate the safety/tolerability and efficacy of 4 sc injections of namilumab 150 mg given over 10 weeks as therapy in subjects with moderate-to-severely active axSpA, including those with a history of inadequate response to or intolerance of anti-TNF therapy. The study will allow enrolment of up to 50% of subjects with primary non-response to prior anti-TNF treatment. The study will consist of a maximum 4-week Screening Period, followed by a 12-week double-blind treatment evaluation period, followed by a 16-week safety follow-up period.

Number of Subjects:

Approximately 70 subjects will be screened to achieve 42 subjects randomly assigned to study treatment (36 on active treatment and 6 on placebo) and 42 evaluable subjects for an estimated total of 36 evaluable subjects on the active treatment arm and 6 evaluable subjects in the placebo treatment arm. Randomisation will be stratified by prior use of anti-TNF agents.

Treatment Groups and Duration: Test product, dose and mode of administration: Namilumab 150 mg sc administered at Day 1 of Weeks 0, 2, 6 and 10. Reference therapy, dose and mode of administration: Matching placebo solution sc administered at Day 1 of Weeks 0, 2, 6 and 10.

 Document:
 x:\biostatistics\documentation\sap\pya18238_izana_izn-101_sap_v1_0_2019050.docx

 Author:
 Version Number:

Template No.: CS_TP_BS016 Revision 5

Effective Date: 01Apr2018

Copyright © 2009, 2010, 2012, 2016, 2018 IQVIA. All rights reserved. The contents of this document are confidential and proprietary to IQVIA Holdings Inc. and its subsidiaries. Unauthorized use, disclosure or reproduction is strictly prohibited.

Version Date:

Page 12 of 36

Table A:Study Schema

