6.5. STATISTICAL TESTS

The default significance level will be 5%; confidence intervals will be 95% and all tests will be two-sided, unless otherwise specified in the description of the analyses.

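### At 36 vs 6, the two-sided Fisher test for the secondary responder endpoints has a true size of at most 2.4%; Boschloo's test is uniformly at least as powerful within 5%, and an effect estimate with an interval should be added

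*SAP*

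**What the plan says.** SAP 14.2.3.1 covers secondary endpoints 1, 2 and 3: ASAS40 at Week 12, ASAS20 at Week 6, and ASDAS-CRP response at Weeks 6 and 12. It specifies the test, "The secondary endpoints will be analysed by means of the Fisher exact test (to account for the small size of the placebo sample"), and the hypothesis, "The null hypothesis is that there is no difference in the response rate between the two treatments". It names no effect measure and no interval. The level comes from SAP 6.5: "The default significance level will be 5%; confidence intervals will be 95% and all tests will be two-sided", unless a section says otherwise, and 14.2.3.1 does not.

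The arm sizes come from Protocol 9.2, "The recommended sample size is 42 (6 on placebo, 36 on active"), and SAP 3.1 repeats them with no allowance for dropout: "42 evaluable subjects for an estimated total of 36 evaluable subjects on the active treatment arm and 6 evaluable subjects in the placebo treatment arm". SAP 14.2.2 adds "Subjects with missing primary endpoint data (either at Baseline or Week 12) will be treated as non-responders", so the denominators in the full analysis set stay at 36 and 6.

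Protocol 9.4.1 (Table 11) names no test for these endpoints: "Summary statistics of ASAS20, ASAS40 and other efficacy endpoints will be summarised by visit" and treatment group. SAP 7.1 gives counts and percentages for categorical variables by default.

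**The concern.** The SAP picks Fisher because the placebo arm is small. Yet a small arm is where conditioning on the total number of responders costs most. With 6 placebo subjects the conditional distribution has at most seven points, and the attainable p-values jump across 5%. If the true size is well below 5%, power is lost for nothing on endpoints that already have little of it.

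With no planned estimate or interval for the difference, the between-arm result is a p-value that will usually exceed 0.05 even when the drug works. A reader could take that as evidence of no effect on ASAS40, when the data exclude very little. SAP 7.5 also says the endpoints are analysed hierarchically, so a conservative early test may hold back later ones.

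**Working it through.** **Inputs.** 36 and 6 subjects (Protocol 9.2, SAP 3.1); two-sided 5% (SAP 6.5); design rates from the Protocol 1.1 synopsis, "assuming true response rates of 0.3 and 0.6 for the control and namilumab arms, respectively"; pooled historical placebo rate 0.34 (Protocol 9.1). Neither document states a size or power for the Fisher test, so there is no figure of that kind to reproduce. The 36/6 split itself can be recovered: the Protocol 9.2 rule at γ = 0.90 gives 42 if the placebo rate is taken as 0.34. It gives 28 at the stated 0.3. That does not affect what follows, which uses only the planned arm sizes.

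**Step 1: where Fisher rejects.** For x responders of 36 and y of 6, with m = x + y, the placebo count is hypergeometric under the null. The two-sided p-value sums all outcomes no more likely than the observed one. The denominator is C(42,6) = 5,245,786.

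- 17/36 vs 0/6 (m = 17): y = 0 has C(25,6) = 177,100; y = 5 has C(17,5) × 25 = 154,700; y = 6 has C(17,6) = 12,376. p = 344,176 / 5,245,786 = 0.066, not rejected.
- 18/36 vs 0/6 (m = 18): y = 0 has C(24,6) = 134,596; y = 6 has C(18,6) = 18,564. The y = 5 outcome is now more likely than the observed one and drops out. p = 153,160 / 5,245,786 = 0.029, rejected.

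One more responder takes p from 0.066 to 0.029. Jumps like this produce the conservatism.

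**Step 2: true size.** There are 37 × 7 = 259 tables, and Fisher rejects 96. Size(π) is the sum over rejected tables of b(x; 36, π) · b(y; 6, π), where b is the binomial probability and π the common rate. The maximum is 0.0241, at π = 0.5. For π from 0.1 to 0.9 it lies between 0.0225 and 0.0241. 0.0241 / 0.05 = 48%.

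**Step 3: Boschloo.** Take the Fisher p-value f as the statistic and use p_B = max over π of P(Fisher p ≤ f). Fisher is itself valid, so p_B ≤ f and every Fisher rejection is kept. At 36 vs 6, Boschloo rejects 108 tables (96 + 12), with maximum size 0.0485. At 17/36 vs 0/6, p falls from 0.066 to 0.032.

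Smallest namilumab count that rejects in its favour:

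| Placebo responders | Fisher | Boschloo |
|---|---|---|
| 0/6 | 18 | 15 |
| 1/6 | 24 | 23 |
| 2/6 | 28 | 27 |
| 3/6 | 32 | 31 |
| 4/6 | 35 | 35 |
| 5/6 or 6/6 | none | none |

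**Step 4: power.** Sum b(x; 36, p₁) · b(y; 6, p₀) over the rejected tables.

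| Namilumab vs placebo | Source of rates | Fisher | Boschloo | Gain (points) |
|---|---|---|---|---|
| 0.60 vs 0.30 | Protocol design, ASAS20 | 19.4% | 24.8% | 5.4 |
| 0.60 vs 0.34 | Pooled placebo rate | 14.9% | 19.6% | 4.7 |
| 0.50 vs 0.20 | Assumed | 16.1% | 25.7% | 9.6 |
| 0.45 vs 0.15 | Assumed | 12.8% | 27.6% | 14.8 |
| 0.40 vs 0.10 | Assumed | 7.8% | 25.7% | 17.9 |

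The assumed rows illustrate a stricter criterion such as ASAS40. The documents give no ASAS40 rates.

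**Step 5: is any unconditional test better?** No. The plain pooled-Z test (the usual Barnard form) rejects 82 tables, all of which Fisher also rejects. Its maximum size is 2.0%, and its power at 0.60 vs 0.30 is 11.8% against Fisher's 19.4%. With a Berger-Boos restriction (0.001) it reaches 28.7% at size 4.87%, but it then no longer contains Fisher's rejection region.

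**Step 6: other arm sizes.** Fisher's maximum size is 2.37% at 35/6, 2.11% at 36/5 and 2.56% at 35/5.

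**The case against.** Fisher is a valid test, the SAP gives its reason, and some statisticians prefer to condition. These are secondary endpoints in a proof-of-concept study whose main decision is Bayesian. All of that stands: the point is about efficiency and reporting, not validity.

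Four stronger readings are tempting, and the documents do not support them.

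- A reader might infer that only a p-value will be reported. Protocol Table 11 and SAP 7.1 provide arm-level counts and percentages. What is missing is a between-arm difference with an interval.
- A reader might blame Fisher because it cannot favour namilumab when 5 or 6 placebo subjects respond. Boschloo cannot either. That limit comes from having 6 placebo subjects.
- A reader might expect the new test to cure the low power. In the scenarios above Boschloo still misses in 72% to 80% of trials, and at the documented design rates it gains only 5.4 points.
- A reader might see an undisclosed departure from the protocol, because SAP 3.3 does not list the added tests. Protocol 9.4 describes itself as a summary and leaves detail to the SAP, so an added test is better read as elaboration.

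**Conclusion.** The point holds. At the planned 36 vs 6, the specified Fisher test uses at most 2.4% of its 5%, and Boschloo's test dominates it at a maximum size of 4.85%. The gain is 5.4 points at the only design rates in the documents and about 10 to 18 points at the assumed lower rates. The statement that less than half of the level is used belongs to the planned arms; at 35/5 the figure is slightly above half. The figure of 12 extra tables belongs to the version of Boschloo that orders tables by the two-sided Fisher p-value described in Step 1.

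The missing effect estimate and interval matter at least as much as the choice of test. With 6 placebo subjects, p > 0.05 is the likely result even for a real effect, and only an interval shows how little has been excluded.

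**What to change.** In SAP 14.2.3.1:

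1. Replace Fisher with Boschloo's unconditional exact test, two-sided at 5%, and state that the ordering statistic is the two-sided Fisher p-value. This needs stating because other two-sided constructions of Boschloo give 23.8% to 27.9% power at 0.60 vs 0.30. Do not offer plain pooled-Z Barnard as an alternative.
2. For each secondary endpoint and time point, report the difference in response proportions with a 95% exact unconditional confidence interval, and say which statistic is inverted to obtain it.
3. State that p > 0.05 will not be read as absence of effect.

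The cost is a few lines of SAP text and a short, validated enumeration of 259 tables, repeated for the per-protocol denominators. The design and data collection do not change. Fisher's p-value can be kept as a supportive result for readers who prefer a conditional test.
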